7.1.5 Equipment to be used for assessing the clinical investigation variables

No specific equipment is required for the conduct of the study.

7.1.6 Any procedures for the replacement of subjects

Not applicable.

7.1.7 Investigation sites: number, location

The clinical investigation will be conducted in 8 sites in Bulgaria. All investigators are familiar with acute infectious rhinitis and study procedures.

7.1.8 Definition of the completion of the study

This is defined as the date of last patient last visit (LPLV).

7.2 Investigational device and comparator

7.2.1 Description of the exposure to the investigational device

The investigational device will be **Healsea® Babykids.** This is a CE marked Medical Device used for acute rhinitis and administered by spraying 2 puffs in each nostril 2 times per day with a minimum of 7-day-treatment period (14 intakes of the investigational device) up to 10 days (20 intakes of the investigational device). The patient should stop taking the investigational device before D11 only if the guestion 1 "not sick" of the ARSSQ is ticked YES for 2 consecutive days.

7.2.2 Description and justification of the choice of the comparator

Clinical batches are manufactured by C.O.C Farmaceutici and the blinding of the investigational devices is ensured by Creapharm, [name], Email: [contact].

The comparator is an isotonic saline nasal spray indistinguishable from the Healsea® Babykids product.

We hypothesize that isotonic saline solution and Symbiofilm[™] will be more effective that the isotonic saline solution for achieving the principal action, i.e. reduction of the duration of acute rhinitis symptoms.

We have chosen isotonic saline solution as Placebo which can be considered as inert solution; nevertheless, nasal irrigation with isotonic saline solution is known to have some efficacy in reducing common cold symptomatology. Posology, instructions for use, contraindications, precaution of use and labelling are identical to those for Healsea® Babykids.

7.3 Subjects

The target population is children (>2, \leq 6 years) with early symptoms of common cold / acute infectious rhinitis.

7.3.1 Eligibility Criteria

7.3.1.1 Inclusion Criteria

Subjects will be enrolled if they meet all of the following criteria:

- 1. Male/Female subjects >2 and ≤6-year-old
- 2. Acute infectious rhinitis/rhinosinusitis for ≤48h before trial entry
- 3. Patient presenting with fever ≥ 37.5 °C at screening
- 4. Subjects with nasal congestion (blocked / stuffy nose) rated at least as moderate on the Acute Rhinitis Symptoms Severity Questionnaire, based on evaluation by the investigator
- 5. Subjects showing at least moderate grade for at least one of the following additional signs of acute rhinitis: runny nose, nasal crust (dry mucus), sneezing and cough
- 6. Written consent obtained from parent/legal guardians

7.3.1.2 Non-inclusion Criteria

Subjects will not be enrolled if one of the following criteria is present:

- 1. Known hypersensitivity/allergy to any component of the test device
- 2. Medical history that is considered by the investigator as a reason for non-inclusion,
- 3. Severe nasal septum deviation or other condition that could cause nasal obstruction such as the presence of nasal polyps
- 4. History of nasal or sinus surgery that in the opinion of the investigator may influence symptom scores
- 5. Antibiotic intake within 2 weeks before screening
- 6. Systemic corticosteroids within 4 weeks before screening
- 7. Chronic decongestant use
- 8. Recent (within the previous 2 days) intake of a common cold medicine that in the opinion of the investigator may influence ARSSQ score at screening (NSAID, nasal decongestants, cough medicines)

7.3.1.3 Withdrawal Criteria and procedures

The reasons for a subject's premature withdrawal from the study may be the following:

- A parent/legal guardian can withdraw his/her consent from the study for any reason at any time but he/she must inform the investigator. In all cases, whenever possible, the investigator should attempt to contact the parent/legal guardian as soon as possible for a final assessment in order to:
 - Obtain the reason(s) for withdrawal and report it/them in the Case Report Form,
 - Evaluate the patient's clinical condition,
 - o If necessary, take appropriate therapeutic measures: management of an adverse effect or concomitant disease, prescription of another treatment.

An investigator may discontinue or withdraw a participant from the study for the following reasons:

- If any clinical adverse event, incident or other medical condition or situation occurs such that continued participation in the study would not be in the best interest of the participant
- If the participant meets an exclusion criterion (either newly developed or not previously recognized) that precludes further study participation. The monitor will be immediately informed by phone or e-mail A letter or report explaining the withdrawal will be forwarded to the monitor as soon as possible.

In these cases, a premature end of study visit will be scheduled. Available data will be retained for the safety/efficacy analysis.

It should be noted that COVID-19 is not an exclusion criterion. Nevertheless, the investigator may consider on a case-by-case basis that a subject should be withdrawn from the study prematurely.

7.3.1.4 Subject lost to follow-up

If a parent/legal guardian cannot be contacted to collect follow-up information even beyond the 7 days from visit 2, the patient will be considered "lost to follow-up". But before declaring that a patient is

Version 1.1 –2023.02.02 Page **34** of **64**

"lost to follow-up", the Principal Investigator (or his/her team) must do his/her best effort to contact parent/legal guardian and attempts should be made via all available routes.

The methods used to attempt contacting the parent/legal guardian should be noted in the patient medical file.

7.3.1.5 Subject replacement

It is not anticipated to replace withdrawal patients.

7.3.2 Point of enrolment and randomization

The subjects will be recruited by the sites among outpatients coming in consultation because of early symptoms of common cold.

The study participation can be proposed to parents/legal guardians of children coming for consultation.

In order to facilitate the enrolment, the site may choose to inform parents/legal guardian of this clinical investigation before this visit.

Before performing any study procedure, the investigator will give all the information pertaining to the study. Parents/legal guardians will have the opportunity to carefully review the information document and ask questions prior to accepting or not to participate in the study. The children will also receive an information specific to their age. The subject will be enrolled in the study just after the consent signature.

7.3.3 Total expected duration of the clinical investigation

The total study duration is planned to be 4 months.

7.3.4 Expected duration of each subject's participation

The duration of each patient's participation is up to 18 days.

7.3.5 Number of subjects required to be included in the clinical investigation

A cohort of 200 patients is expected to participate in the study.

7.3.6 Estimated time needed for the enrolment

Based on the number of participating sites, an enrolment period of 3 months is considered sufficient to enrol the cohort of 200 patients.

7.3.7 Relationship of investigation population to target population

Healsea® Babykids will be used within its intended use, in children above 2 years with acute infectious rhinitis. This post-market clinical investigations aims to demonstrate that isotonic saline solution and

Version 1.1 –2023.02.02 Page **35** of **64**

Symbiofilm[™] act in a synergistic manner to alleviate symptoms of the acute rhinitis phase resulting in better efficacy than isotonic saline solution without Symbiofilm[™].

7.3.8 Vulnerable, pregnant and breastfeeding population

Patient under tutorship or legal guardianship are not eligible.

Pregnant and breastfeeding women: not applicable because it is a paediatric observational study.

7.3.9 Compensation

A compensation of 200 BGN for costs resulting from participation in the clinical investigation (transportation, absence of work...) will be paid to the parents of each patient having completed the study (diary completion and availability for visits).

7.4 Procedures

7.4.1 Description of clinical investigation-related procedures

The clinical investigation is divided into 2 parts:

- Part 1 (D1-D11): treatment of the acute phase with Healsea® Babykids/Placebo, with a minimum of 7-day-treatment period (14 intakes of investigational device) up to 10 days (20 intakes of investigational device).
- Part 2 (up to D15/D18): follow-up phase.

The clinical investigation comprises 2 visits.

Visit 1 (V1) - (Day 1): Screening/Inclusion/Randomization

Parents/legal guardians of children with symptoms of acute infectious rhinitis for ≤48h will go to the site for the screening/inclusion visit (visit 1). The investigator will give oral information relative to the study and will answer all questions relative to the study participation. Appropriate information using drawings will be also delivered to the child. If both parents/legal guardians agree that their child participate in the study, they will receive the information sheet and will be also asked to give a written consent. In case one parent should not be available for the visit; he/she will be asked to confirm in writing that he/she agrees with the participation of the child in the study. Each screened subject will be assigned a subject identifier number during screening that will be used on all subject documentation. The subject identifier number will contain the site number and the subject number and will be assigned in numerical order at the screening visit based on chronological order of screening dates (e.g., 01-010 for the 10th subject screened at the Site #01).

The investigator or his/her delegated designee will:

- Record demographic data, medical history and ongoing medication.
- Perform a physical and clinical examination.
- Instruct the parents/legal guardian of the patient to complete the baseline ARSSQ questionnaire, The investigator/designee will then rate patient nasal congestion symptoms and additional signs of acute rhinitis (runny nose, nasal crust, sneezing, cough)

Version 1.1 –2023.02.02 Page **36** of **64**

- Verify that eligibility criteria are fulfilled.
- Explain to the parents/legal guardians how to complete every day the paper diary ARSSQ recording, how to report concomitant medications, adverse events/incidents.
- Remind the parents/legal guardians to return the device for assessment of compliance to the treatment at V2 and to bring back the paper diary at the study end.

The investigator will provide the parents/legal guardians with the device according to the site specific treatment list, in order to respect the 1:1 randomization (blocks of 4). The investigator will explain how to use it.

NB: The first use of the device will be performed in the evening of the Day 1.

D1-D8 up to -D11 (at home):

The Parent/legal guardian will be asked to complete the ARSSQ in the diary, once daily in the evening. The symptoms occurring from the morning to the evening should be taken into consideration. The ARSSQ shall be scored at least from D1 to D8. Adverse events/incidents and concomitant medications are to be reported during the whole period

Between D8 and D11 (at home):

End of Healsea® Babykids/Placebo nasal spray.

➤ NB: The last study nasal spray intake will be performed **between D8 and D11** in the morning. The patient should stop taking the investigational device before D11 only if the question 1 "not sick" of the ARSSQ is ticked YES for 2 consecutive days.

Up to D15/D18 (at home):

Parents/legal guardians will continue to complete the paper diary daily (incidents/adverse events/expected undesirable sides effects, concomitant medications). For patients for whom common cold symptoms persist, parents/ legal guardians will be instructed to continue to complete the ARSSQ, until the subject feels not sick for two consecutive days.

Visit 2 (V2) - (Day 15-Day 18): end of study

The investigator or his/her delegated designee will:

- Perform a physical and clinical examination.
- Collect the patient diary.
- Review the paper diary to validate adverse events pertinent in the context of the common cold, incidents linked to medical device use and concomitant medications reported by the parents/legal guardians. Complete the e-CRF accordingly and report any new relevant safety events
- Ask parents/legal guardians to complete the ARSSQ if the patient still has symptoms.
- Assess the compliance to the treatment by weighing the device bottle returned by the parents/legal guardians. If a nasal spray is not returned or lost, the investigator will ask the

Version 1.1 –2023.02.02 Page **37** of **64**

Study Number: LPH-2202

parents/legal guardians to specify the number of missed nasal spray uses and will report the data into the e-CRF.

7.4.2 Concomitant Medication

7.4.2.1 Permitted concomitant medications during the study:

- Antipyretics
- Systemic and/or local mucolytics
- Local decongestants (to be taken away from nasal score assessment, 2 hours minimum)
- Systemic antihistamines only if taken for more than 4 weeks at screening
- Antitussive
- Antibiotics
- Local or systemic corticosteroids

C

7.4.2.2 Non-permitted concomitant medications:

Saline nasal spray

7.4.3 Activities performed by sponsor representatives (excluding monitoring)

The sponsor has delegated to the CRO the provision of tasks relative to the project management, medical writing, clinical operations, data management and statistics, and site(s) oversight. These delegated tasks have been established through a Study Management Plan, signed by both parties.

The CRO will rely on its in-force Quality Management System to ensure that the clinical investigation is conducted and monitored, and that data are generated, documented, recorded, evaluated and reported in compliance with the ISO 14155:2020, the CIP, any subsequent amendment(s) and any other applicable standards and in accordance with the regulation requirements. The CRO will ensure the management of ongoing risk in close collaboration with the sponsor throughout the clinical investigation and will take all measures to protect rights, safety and well-being of patients who participate in the study.

Tasks still under sponsor responsibility:

- Reporting of non-compliance trends and safety issues to the Ethics Committee/Competent Authorities and investigators.
- Triggering audit to be performed if applicable.
 - 7.4.4 Any known/foreseeable factors that can compromise the outcome of the clinical investigation and methods for addressing these factors

There is no known/foreseeable factor that can compromise the outcome of the clinical investigation.

Version 1.1 –2023.02.02 Page **38** of **64**

Study Number: LPH-2202

7.4.5 Follow-up and medical care after completion of the study

The patients will receive all treatments needed if the common cold is not cured or in case of complication or safety issues. In this case, the patient will be followed until the end of the issue.

7.4.6 Potential use of samples obtained from subjects

Not applicable.

7.5 Monitoring plan

A risk-based monitoring plan included in a separate document will describe in detail who will conduct the monitoring, at what frequency monitoring will be done, at what level of detail monitoring will be performed, and the distribution of monitoring reports. Results of the risk assessment will be used to develop a risk-based monitoring plan and a supporting rationale.

7.5.1 Initiation visit

The study will only start at a site after:

- The Ethics Committee has granted approval and the Competent Authority has been notified for the conduct of the study,
- Essential documents are in place, such as CVs of the Investigators and site staff, and the Clinical Trial Agreement signed.

In agreeing to participate, the investigator undertakes to strictly comply with the study protocol, Good Clinical Practice, the Bulgarian regulation and to MDR. Investigator also guarantees the authenticity of the data collected in the context of the study and agrees to the legal provisions for study sponsor quality control.

7.5.2 Monitoring

Study monitoring delegated by Lallemand Pharma AG to the CRO will be performed at various stages of the study. Monitoring will include on-site visits and centralized data review to ensure that the investigation is conducted according to the CIP and comply with applicable regulations and deadlines. On-site review of electronic Case Report Form (e-CRFs) will include the review of forms for completeness, clarity, and consistency with source documents available for each subject. In case of queries, investigators should respond within agreed timelines.

Investigators must permit study-related monitoring visits, audits review by the Ethics Committee, and Competent Authority and allow direct access to source data and source documents provided that subject confidentiality is protected. In case of an audit initiated by Lallemand Pharma, the investigator will receive written notification in advance.

Version 1.1 –2023.02.02 Study Number: LPH-2202

7.5.3 Routine Close-out

Routine close-out procedures will be conducted ensuring that the PIs records are complete, all documents needed for the sponsor files are retrieved, remaining clinical investigation materials are disposed of, previously identified issues have been resolved.

7.5.4 Retention of Documentation

Principal Investigators will retain all copies of the records for a period of 10 years from the completion of the clinical investigation. In any circumstances, PIs must contact the sponsor prior to disposing of any records related to the clinical investigation. Should the data be no longer required for regulatory purposes then the confidential destruction of said documents will be approved. Should the data be maintained for longer, Lallemand Pharma AG will make this information available to all appropriate bodies in the same way. A list of essential documents to be maintained will be provided to each site at initiation.

Should a PI have to move/retire, or otherwise leaves his(her) position, he(she) will provide Lallemand Pharma AG with the name and address of the person assuming responsibility for records relating to this clinical investigation.

8. Statistical design and analysis

The statistical analysis will be detailed in the Statistical Analysis Plan. This section provides a summary.

8.1 Analysis population

The safety population consists in all the patients included in this study who will have used the nasal spray at least once.

Full Analysis Set (FAS): all subjects who will have used the nasal spray at least once and with at least one post-baseline efficacy data.

Safety endpoints will be assessed on the safety population.

The analysis of primary and secondary endpoints will be performed on the FAS population.

8.2 Baseline Characteristics

Variables will be described according to the appropriate summary statistics, e.g.:

- Number and percentages of subjects in each category for categorical data. For tabular summaries of percentages, the denominator (e.g. number of subjects with non-missing data) will be displayed.
- Number of observations, mean, standard deviation, median, and range for continuous data.
- Number of observations, number of events, median time for time to event data.

When calculating treatment effects (e.g. differences, hazard ratios, odds ratios) and when using treatment arm as a covariate in regression modelling, the Placebo arm will be used as the reference group.

All statistical tests will be 2-sided and performed using a 0.05 significance level.

8.3 Primary endpoint

In order to analyze the primary endpoint, a multivariate regression model of the AUC of the global score of the ARSSQ during the first 11 days will be used.

8.4 Secondary endpoints

A Cox survival regression model will be used to analyse the secondary endpoints of **duration of cold symptoms and of impact on quality of life**.

A multivariate Poisson regression model will be used to analyse the secondary endpoint related to the **number of days of use of conventional common cold medications** (overall and by therapeutic class).

A multivariate logistic regression model will be used to analyse the secondary endpoint related to the use (yes/no) of conventional common cold medications (overall and by therapeutic class).

-Safety: Adverse events/ incidents will be summarized by the number of occurrences, the number and percentage of patients by treatment group, classified by System Organ Class and Preferred Term as defined by MedDRA dictionary. Only treatment-emergent events will be analysed.

Frequency and percentage of patients with at least one reported adverse event/ incident / expected side effects will be tabulated by System Organ Class and by treatment group.

8.5 Sample Size calculation and justification

See 6.4

8.6 Rationale for the number of procedures to be performed by a single user

Only non-burdensome and non-invasive procedures are planned in the study investigation, mainly a short questionnaire. Two visits are scheduled to assess the study criteria.

8.7 Interim analysis

Not applicable.

8.8 Management of bias (randomization, blinding)

See section 7.1.2

8.9 Management, justification, and documentation of missing data, including drop-outs

For subject who stop completing the ARSSQ before D11 (see 7.4), the Last Observation Carried Forward (LOCF) imputation will be used. Other missing data for the primary endpoint (ARSSQ) will be estimated by interpolation.

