	The primary endpoint is the AUC of the global score of the Acute Rhinitis Symptoms Severity Questionnaire (ARSSQ) over the first 11 days of symptoms.	
	The ARSSQ will be assessed once daily in the evening from Day 1 to Day 8 and, if needed, until complete resolution of all symptoms for 2 consecutive days ("not sick" at question 1 of the ARSSQ). Due to the study schema, data may be censored at Visit 2 (between Day 15 and Day 18 after inclusion).	
	Secondary Endpoints:	
	- Duration of each cold symptom as reported in questions 2 to 7 of the ARSSQ	
	(refer to table 1). For each separate symptom, the duration is defined as the number of days between Day 1 and the first day the parent reports the patient not having this symptom ("Not present") for 2 consecutive days.	
	As mentioned for primary endpoint, duration may be censored at Visit 2.	
	- Duration of quality-of-life impairment as reported in questions 8 to 10 of the	
	ARSSQ. For each separate activity, the duration is defined as the number of days between Day 1 and the first day the parent reports no impact on the patient quality of life ("No impact") for 2 consecutive days.	
	As mentioned for primary endpoint, duration may be censored at Visit 2.	
	- Frequency and number of days of use of concomitant treatments that may	
	affect common cold symptoms (antibiotics, antipyretics, systemic or local	
	mucolytics, decongestants, antitussives, systemic and topical corticosteroids).	
	- Safety: Assessment of adverse event related to acute rhinitis and incidents	
	throughout the study.	
Indication:	Treatment of acute rhinitis in children 2-6 years old	
Investigation Design:	Prospective, Double-Blind Placebo controlled randomized trial	
	The study will comprise 2 parts:	
	- Part 1 (D1-D11): treatment of the acute phase	
	 with Healsea® Babykids, 2 puffs in each nostril 2 times per day with a minimum of 7-day-treatment period (14 intakes of Healsea® Babykids) 	
	up to 10 days (20 intakes of the investigational device).	
	with isotonic nasal spray (Placebo) , 2 puffs in each nostril 2 times per	
	day with a minimum of 7-day-treatment period (14 intakes of Placebo) up to 10 days (20 intakes of the investigational device).	
	- Part 2 (up to D15/D18): follow-up phase.	

Visit 1 (V1) - (Day 1): Screening/Inclusion/Randomization

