6.4.6. Scores of ARSSQ

To compute any score of ARSSQ, if the questionnaire has been completed at a given time point except some items, these missing answers will be imputed by the last observation carried forward (LOCF).

At time points the questionnaire has not been completed at all, no imputation will be done and the score will be missing.

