6.4.7. AUC on global score of ARSSQ

The computation of the AUC on global score of the questionnaire will be made for patients with non-missing value at D1 and at least another non-missing time point between D2 and D11. Otherwise, the AUC will be missing.

The AUC will be computed by the trapezoidal rule from D1 to D11 (Acute Phase).

If the value at D11 is missing, then it will be estimated by the value at the last non-missing time point before D11.

AXIODIS CRO 13/47

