12. CHANGES IN THE CONDUCT OF THE STUDY OR PLANNED ANALYSIS

The planned analysis in the protocol to assess the primary objective (multivariate ANCOVA model of the AUC on global score of ARSSQ during the first eleven days of the study) has been replaced by the comparison of the means of the AUC on global score of ARSSQ during the first eleven days of the study between treatment groups. The multivariate ANCOVA has been put among secondary analyses.

This change has no impact on the relevance of the sample size calculation since the primary endpoint is the same as planned in the protocol.

Moreover, since several patients still reported having symptoms while they reported they did not feel sick anymore at the question 1 during at least the two last days of completion of the ARSSQ, their positive answers to the cold symptoms' items have been considered as non-significant. Consequently, the question 1 has been taken into account in addition to the corresponding items to determine the end of the cold symptoms' duration, however only on the condition that the last days of completion were consecutive.

If the last days of completion were not consecutive, positive answers to cold symptoms' items are still considered as symptomatic, even if the two last answers to the question 1 are negative. The symptom ends at the last symptomatic day if the patient reported the absence of this symptom at least twice and consecutively after this day. Otherwise, the duration of the symptom is censored at D18 or at the end of the study, whichever occurs first.

The same change has been applied to compute the duration of impact on QoL.

AXIODIS CRO 25/47

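### For a child with a diary gap covering D11 and a later ARSSQ score, the SAP carries the earlier score forward where the protocol calls for interpolation, and the SAP does not declare the difference (minor)

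*Protocol*

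**What the plan says.** The primary endpoint is the AUC of the ARSSQ global score over 11 days (Protocol synopsis; SAP 6.4.7 and 10.1).

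Protocol 8.9 has two rules for missing scores. The first is for children who stop: "For subject who stop completing the ARSSQ before D11 (see 7.4), the Last Observation Carried Forward (LOCF) imputation will be used". The second covers everything else: "Other missing data for the primary endpoint (ARSSQ) will be estimated by interpolation".

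SAP 6.4.7 computes the AUC by the trapezoidal rule from D1 to D11 and has a single rule for the end point: "If the value at D11 is missing, then it will be estimated by the value at the last non-missing time point before D11". It sets no condition on whether a later score exists. For any other unanswered day, SAP 6.4.6 says: "At time points the questionnaire has not been completed at all, no imputation will be done and the score will be missing".

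Scores after D11 are part of the design. Under Protocol 7.1.3 and 7.4.1 the diary continues daily after D8 until the child has been 'not sick' on two consecutive days. At V2 (D15 to D18) the site must do this: "Ask parents/legal guardians to complete the ARSSQ if the patient still has symptoms".

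SAP 12 lists two changes from the protocol: the primary test, and the way symptom and quality-of-life durations end. The D11 rule is not among them.

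**The concern.** A child who is still ill can miss D11, or D9 to D11, and then resume the diary at D12. That child has not stopped completing the ARSSQ, and the missing D11 lies between two observed scores. The protocol interpolates; the SAP ignores the later score and holds the earlier one flat to the end of the AUC window.

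Such gaps are foreseen. SAP 7.2 counts ARSSQ data missing before recovery as a minor deviation if D1, D5±1 and D8-1 are available, so these children stay in both the FAS and the PP set. SAP 12 also provides for last completion days that are not consecutive.

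At stake is that the only confirmatory endpoint (SAP 6.3.1) is defined in two ways for identifiable children, so two analysts could compute different AUCs from one diary. Protocol 8.10 expects departures from the planned analysis to be reported.

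**Working it through.** **The plan's own figure.** The documents give no figure for the imputation. The sample size reproduces: for d = 0.4, two-sided 5% and 80% power, the normal approximation gives 99 per arm, and 100 per arm gives power 0.807 (0.804 with the noncentral t). This point does not affect it.

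**Where the documents agree.** For a gap strictly inside D1 to D11, the trapezoidal rule joins the two neighbouring scores by a straight line, which is linear interpolation. Check with scores 18, 17, 15, 15 on D1 to D4 and 6, 5, 4, 3, 2 on D7 to D11: the AUC is 96.0 both with D5 and D6 left blank and with 12 and 9 interpolated. The documents also agree on LOCF for a child who stops before D11 and has no later score.

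**Where they differ.** Let L be the last scored day before D11, M the first scored day after it, and sL, sM the scores on those days; all days from L+1 to D11 are missing.

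- SAP: D11 = sL, so the area from L to 11 is sL(11−L).
- Protocol: D11 = sL + (sM−sL)(11−L)/(M−L), so the area is sL(11−L) + (sM−sL)(11−L)²/[2(M−L)].
- Difference, SAP minus protocol: **(sL−sM)(11−L)²/[2(M−L)]**.

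The sign is that of sL−sM: positive if the score falls across the gap, zero if flat, negative if it rises.

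**Size.** For a straight-line fall of b points/day, sL−sM = b(M−L), so the difference reduces to b(11−L)²/2. The slopes are assumptions; the documents give none.

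| Missing days | L | b = 0.5 | b = 1.0 | b = 1.2 |
|---|---|---|---|---|
| D11 | 10 | 0.25 | 0.5 | 0.6 |
| D10–D11 | 9 | 1.0 | 2.0 | 2.4 |
| D9–D11 | 8 | 2.25 | 4.5 | 5.4 |
| D8–D11 | 7 | 4.0 | 8.0 | 9.6 |

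For scale, a child starting at 15 and falling 1 point/day has a true AUC of 10×15 − 50 = 100. The SAP gives 100.5, 102.0 and 104.5 for the first three rows; interpolation to D12 gives 100.0 each time. With a rise of 0.5/day the differences for those rows are −0.25, −1.0 and −2.25.

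**With noisy scores.** An illustrative simulation assumed an onset score N(16, 4), exponential decline with lognormal half-life (median 4 days, log SD 0.45), residual SD 1.5, scores rounded and kept within 0 to 30, children scoring at least 2 at D11, and the next score at D12. Mean error against the complete AUC:

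- D11 only: +0.04 (SAP) against −0.2 (interpolation).
- D10–D11: +1.0 against −0.1.
- D9–D11: +2.8 against +0.2.

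**Effect on arm means.** Assume that 5% of one arm only is affected, by 0.5 to 4.5 points each, with an AUC SD of 30. The mean shift is 0.05×0.5 = 0.025 to 0.05×4.5 = 0.225 points, or 0.001 to 0.008 SD, against a design effect of 0.4 SD. Power at d = 0.4 would move from 0.807 to between 0.806 and 0.793. If both arms are affected alike, the shift cancels on average.

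**The case against.** The strongest reply is that nothing here threatens the result. The same rule is applied blind to both arms, and nothing in the documents suggests that gaps, or the slope across them, differ by arm. That stands. A reader might infer that the rule biases the treatment effect; the documents do not support it.

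A reader might also infer that the AUC of every still-ill child with a gap at D11 is overstated. That goes too far as well. Protocol section 4 describes colds as generally self-limiting but also describes recurrence and worsening. In the simulation, 41% of children with only D11 missing had a D12 score at or above D10, so the SAP value was no higher than the interpolated one, and the SAP rule had the smaller mean error for that gap.

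Three further replies have force:

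- **V2-only scores.** A family that abandons the diary at D8 and fills in the questionnaire at V2 on request can be read as having stopped, which makes LOCF the protocol's own rule. But 8.9 points to 7.4, where completion ends on recovery, and on that reading a still-ill child falls under interpolation. The text does not settle it, so the clear conflict is limited to diaries that resume at D12 or later.
- **SAP 12.** Its statement "since the primary endpoint is the same as planned in the protocol" defends keeping the sample size after the change of test. It should not be read as a claim about imputation. What can be said is that SAP 12 omits the D11 rule.
- **Summary status.** Protocol section 8 calls itself a summary to be detailed in the SAP, and using only data inside D1 to D11 is a defensible convention. But 8.9 states a specific rule, and the SAP replaces it for these children rather than adding detail.

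**Conclusion.** The inconsistency is real, narrow and undeclared. For a still-ill child whose diary has a gap covering D11 and resumes at D12 or later, SAP 6.4.7 discards an observed score that Protocol 8.9 would use. The direction depends on the course across the gap. The size is negligible for D11 alone and a few AUC points for a three-day gap.

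The documents do not give the number of such children, the score slopes or the AUC SD, so the sizes rest on the assumptions stated with them. On those assumptions the effect on arm means is very small. Severity: minor. The reason to act is that the confirmatory endpoint should have one definition.

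**What to change.** Replace the D11 sentence in SAP 6.4.7 with:

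> If D11 is missing, the child had not already stopped the ARSSQ after two consecutive 'not sick' days, and the diary resumes after D11, D11 is estimated by linear interpolation between the last score before and the first score after D11. Otherwise LOCF is used.

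The condition on having stopped matters. Without it, a child who recovered, properly stopped at D9, relapsed and was scored again at V2 would have a rising line drawn through D11, where Protocol 8.9 gives LOCF.

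Add a sentence saying which rule applies when the only later score is the V2 questionnaire. If the sponsor prefers the present rule, list and justify it in SAP 12 as a departure from Protocol 8.9.

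The cost is one or two sentences and a line of code. The later scores are already collected, so there is no new data collection and no burden on families.
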